### 7.3.2 Secondary Analyses

Analyses for secondary objectives will be mostly descriptive. Line listings as well as summary descriptive statistics including means, medians, and proportions with 95% exact or asymptotic confidence intervals as appropriate at each visit, will be used for the following secondary objectives. Specifically,

- Use GEE or random effects models to describe longitudinal patterns and their correlates of PrEP adherence among participants (e.g.: substance use, sociodemographics, sociocultural factors, risk practices and incarceration)
- To describe side effects and adverse events of PrEP among participants in the PrEP demonstration project. AEs will be tabulated, overall and by grade. For any reasonably common AEs (> 20 events), exploratory analyses will be conducted to assess correlates of the AE, including demographics and duration and patterns of PrEP use, within the limits imposed by the small expected number of events.
- Describe and produce summary plots for longitudinal changes in sexual risk-taking behavior among study participants
- List and summarize reasons PWID choose to initiate or decline PrEP
- List and summarize HIV seroconversions and characteristics of the infection(s) (e.g., viral set point, drug resistance patterns) in participants who initiated PrEP

- Use Kappa-statistics to assess agreement of adherence under different measures.

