## 1.4 HIV Seroconversion

Incident HIV infections on this study are expected to occur uncommonly, even in the at-risk study population. However, any participant experiencing an incident HIV infection offers the opportunity to assess the impact of the PrEP regimen. Consequently, these participants will discontinue study medication and will be carefully characterized with regard to their HIV RNA level, CD4 cell count and set points over time, as well as antiretroviral drug resistance, and other factors.

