### 5.3 Month 1, 3 and Month 6 (exit visit)

At months 1 and 3, the participants will visit the clinical site to complete the assessments and receive the medication supply for next two (at month 1) three (at month 3) months. At month 6, participants will not receive medication as a part of the study, but will be referred to other available PrEP providers in Kyiv. The following procedures will be included.

- Verify locator information
- Behavioral and psychosocial survey
- Self-reported study product adherence assessment
- PrEP discussion
- PrEP Navigation and study product supply
- Autonomy supportive adherence counseling
- SMS reminder customization

- HIV/ STI behavioral risk-reduction counseling, provision of prevention supplies
- Medical history including but not limited to co-morbidities, concomitant medications, HIV risk history
- Symptom-driven physical exam
- AE Assessment
- HIV rapid test – at months 3 and 6.
- DBS storage for pharmacology testing
- Urine storage for substance use testing

The exit visit will include all procedures for Month 3, except for PrEP provision and related counseling and SMS customization.

#### 5.4 Months 2, 4, 5

Monthly assessments between the PrEP dispensing visits (Enrollment and 3-month) will be conducted by research staff **by telephone**. The following procedures will be included.

- Review and update locator information
- Self-reported study product adherence assessment

Self-reported PrEP adherence for all participants will be assessed using both a visual analogue scale (VAS) and a new 3-item self-report measure. The VAS is empirically validated, consistently under-reports adherence, but effectively measures a “difference” in adherence that changes in response to an intervention. The 3-item adherence self-report scale showed good psychometric characteristics and good construct validity when compared with an drug monitoring standard. Two self-report adherence measures are often recommended.

- PrEP discussion
- Autonomy supportive adherence counseling
- SMS reminder customization

Experimental arm participants will have an opportunity to change the parameters of the SMS reminders.

- HIV/ STI behavioral risk-reduction counseling

After the standard risk-reduction counseling, the participants will be invited to visit the harm reduction site to receive supplies.

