## **5.9 Participants who have Suspected or Confirmed HIV at Screening or During the Study**

In the case of suspected HIV infection at the Screening visit, HIV status will be confirmed using local HIV testing guidelines. Participants who have a reactive or positive HIV test at Screening are not eligible for enrollment, even if subsequent testing indicates that they are not HIV infected.

Participants who have a reactive HIV test result at a follow-up visit will be instructed to discontinue their study medication immediately. According to Ukrainian legislature, HIV diagnosis cannot be made in any setting other than an accredited governmental HIV lab. Therefore, a positive result of rapid testing (regardless of the number of confirmatory runs) will be explained to a subject as preliminary and insufficient to definitively confirm HIV infection, which can be done at specialized health care institutions. As specified in the National HTC guidelines, post-test counseling will provide all details on where the confirmatory testing can be done, and appropriate referrals will be provided.

Any participant who is found to have confirmed HIV infection after Enrollment will be followed at all scheduled visits as described in Appendix I. HIV-infected participants will be followed to contribute information regarding HIV outcomes after PrEP exposure (including viral set point), and to comply with expectations of communities.

HIV-infected participants will also be able to continue receiving assistance in securing HIV medical care. Participants who acquire HIV infection during the study will be asked to provide releases of information that will allow study counselors to consult with providers of HIV medical care to coordinate case management, and to implement other strategies intended to help participants to be retained in medical care and to adhere to treatment regimens. These activities will be logged in PN counselor charts.

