## 7.0 STATISTICAL CONSIDERATIONS

### 7.1 Review of Study Design

This is an open-label, two-site, two-arm, prospective, randomized controlled trial that aims to assess the initiation, acceptability, safety, and feasibility of daily PrEP for PWID in Ukraine with or without SMS reminder intervention. HIV-uninfected PWID aged 18 and over and at risk for HIV infection will be

recruited and enrolled. Each participant will be offered daily PrEP and followed up to 6 months.

Participants will be followed at the specified study time points and will be evaluated for side effects, adherence, risk behavior and HIV-seroconversion.

**Primary Endpoints:** The primary endpoint of this study is the adherence to PrEP.

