#### Incident HIV-seroconversions and characteristics

HIV testing will be performed with confirmation if necessary at all study visits.

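### The seroconversion summary in Section 7.3.2 covers only PrEP starters, so an infection detected in an enrolled non-starter would be missing from the reported count

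*Protocol*

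**What the plan says.** **Endpoint.** Section 7.1 names "Incident HIV-seroconversions and characteristics" as a secondary endpoint and adds: "HIV testing will be performed with confirmation if necessary at all study visits". It also says of participants in general: "Participants will be followed at the specified study time points and will be evaluated for side effects, adherence, risk behavior and HIV-seroconversion". Neither sentence refers to PrEP use.

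**Testing.** Section 5.3 places the follow-up rapid test "at months 3 and 6", and Appendix I agrees. This is narrower than the all-visits wording in Section 7.1, but neither version makes testing depend on PrEP use.

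**Follow-up of infections.** Section 5.9: "Any participant who is found to have confirmed HIV infection after Enrollment will be followed at all scheduled visits". It gives the purpose as learning about HIV outcomes after PrEP exposure. Section 1.4 says that "any participant experiencing an incident HIV infection offers the opportunity to assess the impact of the PrEP regimen" and expects such infections to be uncommon.

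**Who may not be on PrEP.** Section 4.2 leaves the decision to start, and its timing, to the participant. Section 5.2 (PrEP discussion) lists abstaining as an option. Section 7.3.2 itself plans to summarise reasons for declining.

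**Analysis.** Section 7.3.2 has one bullet on this endpoint: "List and summarize HIV seroconversions and characteristics of the infection(s) (e.g., viral set point, drug resistance patterns) in participants who initiated PrEP".

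**The concern.** The trial looks for infections in everyone it enrols and follows everyone it finds infected, but its one analysis statement covers only those who started PrEP. If a non-starter seroconverts, the trial will know of it and the planned summary will leave it out. The reported number would then be lower than the number detected, for the most serious outcome the study records.

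With so few infections expected, a single omitted case could change the summary noticeably. A count limited to starters could also be taken by readers for the count in the whole cohort. By contrast, Section 6.2 assesses adverse events in all participants whether or not they continue PrEP, so the narrower population for seroconversion does not follow a general rule of the protocol.

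**Working it through.** The protocol gives no incidence, event count or precision statement for seroconversion, so there is no stated figure to reproduce. The check is a comparison of text, followed by an illustration of size.

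**Step 1. Populations side by side**

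| Place | Population |
|---|---|
| 7.1, endpoint | No restriction stated |
| 7.1, evaluation for seroconversion | Participants in general |
| 5.3 and Appendix I, HIV test at Months 3 and 6 | No condition on PrEP use |
| 5.9, follow-up after infection | Any participant infected after enrollment |
| 7.3.2, list and summary | PrEP starters only |

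The last row is the narrowest, and nothing else in the protocol covers seroconversions in non-starters. This is a population that the protocol states, not a detail left open for a later plan.

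**Step 2. Size, for illustration**

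Inputs from the protocol: 200 participants (Schema); 6 months, or 0.5 year, of follow-up (7.1); an acceptance rate of 50% in the worked example (7.2); a PrEP effect of about 50% (1.1).

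Assumptions: incidence of 1 to 5 per 100 person-years in non-starters; a share starting PrEP of 33%, 50%, 67% or 90%; equal underlying risk in starters and non-starters.

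Formulas:
- Non-starters = 200 × (1 − share starting)
- Expected omitted infections = non-starters × annual incidence × 0.5
- Omitted share of all infections = non-starters / [non-starters + starters × (1 − effect)]

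| Share starting | Non-starters | Omitted infections, 1% to 5% per year | Omitted share, no PrEP effect | Omitted share, 50% effect |
|---|---|---|---|---|
| 33% | 134 | 0.67 to 3.35 | 67% | 80% |
| 50% | 100 | 0.5 to 2.5 | 50% | 67% |
| 67% | 66 | 0.33 to 1.65 | 33% | 50% |
| 90% | 20 | 0.1 to 0.5 | 10% | 18% |

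Example at 50%: 100 × 0.01 × 0.5 = 0.5 and 100 × 0.05 × 0.5 = 2.5. With a 50% effect the share is 100 / (100 + 100 × 0.5) = 67%.

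The table ignores loss to follow-up. If the 10% to 20% lost (7.2) each contribute half their time on average, total person-time is 100 × 0.95 = 95 down to 100 × 0.90 = 90 person-years. The expected counts then fall by 5% to 10%, for example to 0.45 to 2.4 at 50% starting.

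**The case against.** **The restriction may be deliberate.** Sections 1.4 and 5.9 explain the interest in these infections by exposure to PrEP, and resistance and set point after PrEP are questions about exposed people. This stands for the characteristics. It does not explain leaving an infection in a non-starter out of the count.

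**The qualifier may attach only to the characteristics.** The sentence can be read so that all seroconversions are listed and only their features are limited to starters. That reading is possible but not clear from the text. It means a flat contradiction is not proven; it also means the sentence needs rewording.

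**Non-starters may be few.** The 50% is a single worked example, and the matching table in Section 7.2 labels that column persistence, not acceptance. Section 5.2 has navigators ensure that each participant receives a first supply. This stands, and the 50% row above is not a forecast.

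**Stronger readings that the document does not support.** A reader might infer that selecting on a choice made after randomisation biases a treatment effect. Randomisation is to SMS or no SMS, and this bullet is descriptive and compares no arms. A reader might infer that the report could not tell infections on drug from those off drug. Section 7.3.2 opens with line listings, which show cases one by one. A reader might also call the population everyone randomised. That is too wide: Section 5.2 withdraws those who test positive at the enrollment visit, and Section 5.7 deletes the data of those who choose to withdraw.

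**Conclusion.** The point holds as a matter of reporting population. As written, Section 7.3.2 leaves out of the seroconversion summary any infection detected in an enrolled participant who never started PrEP, although the protocol tests for and follows such infections.

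The omission becomes real only if a non-starter seroconverts. Across the assumed ranges its expected size runs from 0.1 infections (90% starting, 1% per year) to 3.35 (33% starting, 5% per year), before loss to follow-up. Both the incidence and the share starting are assumptions; the indications that most will receive a first supply point towards the lower end. The endpoint is secondary and descriptive, so adherence and persistence results are untouched. It is worth correcting because the correction costs almost nothing and the outcome is serious.

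**What to change.** Replace the bullet in Section 7.3.2 with wording such as:

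> All HIV seroconversions detected after enrollment will be listed and summarised for all enrolled participants, by study arm and by PrEP initiation status (never started; started, with use at the time of infection and the DBS result where available). Viral set point and drug resistance will be described for those who started PrEP.

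The words 'where available' are needed because Section 5.2 allows DBS testing to be limited to a subset of samples; the change should not be read as requiring extra assays.

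Cost: one reworded bullet and a slightly longer listing with very small counts. Infections, arm and initiation status are already recorded. No visit, test or treatment rule changes. Infections among those whose data are deleted under Section 5.7 would still be absent, and the report should say so.

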### 7.3.3 Qualitative Data Analyses

Qualitative data analyses will be conducted on an ongoing basis in collaboration with data collection. Thematic coding will be used to analyze the data from the individual interviews based on a grounded theory approach. The Consensual Qualitative Research Method (CQR) will be used by the study team to analyze the data. The CQR method provides a reliable, systematic, and rigorous method in conducting qualitative data analyses - recognizing the importance of context, incorporating an inductive analytic process, using a team and making decisions by consensus, using auditors, and verifying results by systematically checking against the raw data. The key elements of conducting qualitative data analyses using the CQR method include: (1) develop and code domains, (2) construct core ideas, and (3) develop categories to describe consistencies across cases (cross analysis).

## 8.0 HUMAN SUBJECTS CONSIDERATIONS

The protocol, ICF, participant education and recruitment materials, and other documents and any subsequent modifications will also be reviewed and approved by the Institutional Review Board (IRB) at the Ukrainian Institute on Public Health Policy (Kyiv, Ukraine).

The Investigator will make safety and progress reports to the IRB within three months of study termination or completion. These reports may include the total number of participants enrolled in the study, the number of participants who completed the study, all changes in the research activity, and all unanticipated problems involving risks to human subjects or others.

### 8.1 Informed Consent

Written informed consent will be obtained from each study participant, including both quantitative and qualitative components. Three separate ICFs will be developed for the main study participation (Appendix IIIa), in-depth interviews with participants (Appendix IIIb), and interviews/ focus groups with providers and PrEP Navigators (Appendix IIIc). In addition, the main study participants will be asked to provide a separate written informed consent for their blood specimens to be stored after the end of the study for possible future testing.

For all three procedures, the informed consent forms will be read aloud to each eligible participant by a project team member. All questions that respondents may have will be adequately clarified and explained to them. Potential participants will be informed that their participation in the intervention is completely voluntary and that they have a right to withdraw their consent forms and stop their participation in the study at any time. Refusal or withdrawal from the study at any time will have no effect on the participant's access to health facilities or HIV-related care and treatment, or their employment. Participants will be informed that any information that they disclose during the course of the study will be considered confidential (i.e., no personal identifiers will be used and only aggregated information across all participants will be reported). Participants will have the potential risks and benefits of the study explained to them as well. For all candidates, understanding of the essential parts of the document will be assured by asking questions to verify their knowledge of the study procedures. If a candidate agrees to participate in the study, the candidate, or a witness if a candidate is illiterate, will document provision of informed consent by signing on the consent form. Unsigned copy of consent forms will be offered to the participants

### 8.2 Potential risks

As part of this study, participants will be asked to undergo HIV counseling and testing, provide information about their drug use, provide contact information, and take PrEP medication. Drawing blood for HIV rapid test involves minimal risk, including the possibility of local trauma and infection. Participants will be asked questions about sensitive topics such as drug use. It is possible that some individuals may experience discomfort from taking part in these study activities.

There is a potential risk for participants who are found to be HIV-infected to become distressed after receiving their test results.

Participation in HIV prevention, and PrEP in Ukraine is not associated with any punitive or social risks with the exception of common stigma attached to drug use. This study does not increase the risk of stigma associated with drug use or HIV for participants.

Taking PrEP medication may lead to adverse events or side effects, described in detail in Section 6.

### **8.3 Protection Against Risks**

Participation in the study is completely voluntary and confidential. The unique identifier code, linking all study records is based on information provided by participants verbally, and no documents are requested. It is not possible to identify a person using this code. Contact information will be requested to allow invitation for follow-up assessments, and this information will be kept strictly confidential (see below). Mobile phone numbers in Ukraine in most cases are not personally identifiable information, because prepaid numbers are not linked to any contract or personal registration data.

The study personnel will explain to participants that the information collected in the study may be accessed by the law enforcement entities only in case of an individualized request with regard to an open criminal case.

As part of the informed consent procedure, all potential participants will be instructed that they do not have to disclose personal information which they are uncomfortable sharing and that they can withdraw from the study at any time.

Participants will receive names and contact information of the organizations conducting the study, as well as other study team members, on their copy of the informed consent form. It will be explained to the participant that they may contact anyone on the list if they have any questions or comments regarding the study, if they suffered in any way due to their participation/failure to participate in the study. The participants will be informed that they may refuse to answer any questions that make them feel uncomfortable and that participation in the intervention is voluntary. Absolutely no information on any participants of the study will be given to other participants.

To minimize psychological risk, the recruitment into the study will be done by a trained social worker, and interview will be conducted by a trained interviewer. The interviews will be carried out face-to-face and there will be no additional persons in the room during the interview except the interviewer and respondent. HIV testing and counseling (HTC) will be performed in designated rooms, which meet the privacy requirements set in the national HTC guidelines. Pre-test counseling will be carried out before HIV testing. Participants with HIV positive test results will be informed that final diagnosis will only be given after confirmation testing by the AIDS center laboratory and referred for additional testing. There is a potential risk for participants who are found to be HIV-infected to become distressed after receiving their test results. Study staff is trained to provide HIV post-test counseling to persons newly diagnosed with HIV. Study staff will also be equipped to refer participants who need additional counseling and assistance to community resources, including referrals for HIV care and treatment. Pre- and post-test counseling will be provided by qualified staff only.

All adverse events will be managed as described in Section 6.

### **8.4 Incentives**

Pending IRB approval, participants will be compensated for their time and effort in this study, and/or be reimbursed for travel to study visits and time away from work. The reimbursement amounts will be specified in the study informed consent forms.

### **8.5 Confidentiality**

All study-related information will be stored securely at the study sites and in the main office. All participant information will be stored in locked file cabinets in areas with access limited to study staff. All laboratory specimens, reports, and study data-collection, process and administrative forms will be identified by a coded number to maintain participant confidentiality. All records that contain names or other personal identifiers, such as locator forms and informed consent forms, will be stored with restricted access according to local SOP. All local databases will be secured with password-protected access systems.

Participant study information will not be released without the written permission of the participant, except as necessary for monitoring by the Sponsor, government and regulatory authorities, and/or site IRBs.

## **8.6 Protocol Deviations**

All protocol deviations, new/unexpected findings and changes to the study environment will be documented and immediately reported to the in-country study team who will then notify the Sponsor. If necessary, a formal report will be sent to the appropriate IRBs. Reporting of such incidents will be the responsibility of the Principal Investigators of this study. Any discussions, issues, and complaints related to the study will be reviewed promptly to ensure close monitoring of the impact of the study on participants. Appropriate action will be taken to resolve or deal with all issues accordingly.

